## 9. CLINICAL MONITORING

### 9.1. Site Monitoring Plan by CRO

During the intervention phase, trained clinical trial monitoring experts (e.g. ClimAfrica-CRO or another contract research organization [CRO]) will conduct at least six monitoring visits (before, during and immediately after the intervention phase of the study, each in rainy seasons 1 and 2). These will include assessment of site compliance and standard operating procedures, review of consents, assents, training documents, research/study approvals and data collection forms, review of site facilities, and laboratory sample storage, shipment, and labeling. The study monitor will collate and promptly share their reports with the study investigators and study sponsor. The investigators will provide these reports to the DMID for their assessments of the study's adherence to GCP practices and recommendations and/or considerations of early trial termination due to possible data quality or safety concerns.

## 10. STATISTICAL CONSIDERATIONS

### 10.1. Study Hypotheses

The primary objective hypothesis is that repeated IVM MDAs (the intervention) coinciding with SMC rounds and other standard-of-care malaria control measures (LLIN distribution, IPTp) will significantly reduce the incidence of childhood malaria compared to the placebo intervention. This hypothesis will be tested in a 2-arm superiority trial with a cluster randomized design. The primary outcome measures of incidence of malaria episodes among village children ≤ 10 years of age in each arm will be used to test the hypothesis. The primary objective null hypothesis is that that repeated IVM MDAs coinciding with SMC rounds and other standard-of-care malaria control measures will have no effect on the incidence of childhood malaria compared to placebo MDAs coinciding with SMC rounds and other standard-of-care malaria control measures.

Secondary objective hypotheses:

- The risk of adverse events (AEs) per participant in the intervention arm occurring over the intervention phase of the trial will not differ relative to the risk of adverse events in the control arm.  
*Null: The risk of adverse events (AEs) per participant in the intervention arm occurring over the intervention phase of the trial will not differ relative to the risk of adverse events in the control arm.*
- The survival rates of wild blood fed *Anopheles gambiae* s.l. will be significantly reduced, and age-structure and entomological inoculation rate in wild *Anopheles gambiae* s.l. significantly younger/lower, in those captured from intervention arm villages as compared to those captured control arm villages at equivalent time intervals during the intervention phase. Also, the immuno-reactivity of intervention-arm participants' IgG over time to an *Anopheles* salivary gland peptide will be significantly lower than that from control arm participants.  
*Null: The survival rates of wild blood fed Anopheles gambiae s.l., and parity and sporozoite rates in wild Anopheles gambiae s.l., will not differ in those captured from intervention arm villages as compared to those captured control arm villages at equivalent time intervals during the intervention phase. Similarly, the immuno-reactivity of intervention-arm participants' IgG over time to an Anopheles salivary gland peptide will be no different than that from control arm participants.*
- The *Plasmodium falciparum* multiplicity of infection per episode or blood sample, and number of new *Plasmodium falciparum* clones per unit time per child, will be significantly reduced in intervention arm children compared to control arm children.  
*Null: The Plasmodium falciparum multiplicity of infection per episode or blood sample, and number of new Plasmodium falciparum*

---

*clones per unit time per child, will not differ in intervention arm children compared to control arm children.*

- The concentration of ivermectin in participant's plasma will change over time post-drug administration and vary between age and gender strata. Mosquitoes that feed on recent ivermectin-treated participants will have detectable ivermectin in their blood meals. *Null: The concentration of ivermectin in participant's plasma will not change over time post-drug administration and will not vary between age and gender strata. Mosquitoes that feed on recent ivermectin-treated participants will not have detectable ivermectin in their blood meals.*

## 10.2. Sample Size Considerations

[figure not shown]
The trial design and power calculation is guided by the Malaria Transmission model developed at Imperial College, London (<http://www.imperial.ac.uk/malaria-modelling/tools-and-data/>) and informed by data from our RIMDAMAL I trial as well as the longer mosquitocidal effect (up to 30 days) from the intervention dose and regimen predicted from IVERMAL data. The model suggests we should observe an effect size in the intervention arm over the control arm of 43.1% (Figure 4). This assumes a rate incidence in our 0-10 yr. old cohort of 1.088 malaria episodes/child/year and 0.619 malaria episodes/child/year in the control and intervention arms, respectively. To determine the cluster sample size and cluster population (children cohort size) we used the sample size formula for obtaining the number of clusters in an unmatched CRT design with a 'rate' endpoint (49). The formula uses the coefficient of variation ( $\kappa$ ; SD/mean) of the true rates between clusters within each group, which we estimated in southwestern Burkina Faso to be 0.258 (50). From these variables, and setting the  $\alpha=0.05$  (Type I error rate or probability of detecting a false negative result = 1.96), 6 clusters/arm with a minimum of 48 children/cluster in our child cohort is necessary to detect a significant difference in the rates between the arms with 80% power (Type II error rate or probability of rejecting a false positive result = 0.84). Relatedly, if we instead calculate the cluster population sample size using the intraclass correlation coefficient retrospectively calculated from RIMDAMAL I data (ICC=0.059), and setting the  $\alpha=0.05$ , with 6 clusters/arm the necessary number of children to follow per cluster is 9.

In January 2019, the sample size modeling exercise was re-performed because it was learned that that villages in the Diebougou health district (the study site) were expected to receive new Interceptor G2 LLINs prior to the 2019 rainy season. These new LLINs are made with two different insecticides (chlorphenapyr and alpha-cypermethrin) to circumvent the prevalent pyrethroid-resistance seen in Burkina Faso the much of SSA. Thus, we assumed a 12%-50% reduction in malaria incidence in

both arms due to distribution of these nets. Keeping with an effect size of 43.1% in the intervention arm over the control arm, using an intra-cluster coefficient of 0.2, and increasing the sample size to 100 children/cluster in our child cohort, we need between 4.9 and 5.5 clusters/arm to detect a significant difference in the rates between the arms with 80% power. Given that we will select 7 villages per arm, which are expected to have population sizes of 0-10 year old children of approximately 100, we feel we will have >80% power to reject the null hypothesis if it is false, even if some children drop out of the study or are lost to follow-up.

The primary outcome will be analyzed as intention-to-treat. The incidence of episodes from the children cohort will be used as the primary measurable outcome to evaluate the impact of the intervention when compared to the control arm. The primary analysis will use either cluster-level analyses, or multilevel/hierarchical regression modeling techniques to account for clustering at the level of the randomization unit (village), as well as analyze individuals with multiple time points. and comparisons using a critical value of  $\alpha$  at 0.05. The analysis may need to be corrected to account for the relatively few number of clusters in the study design. The unadjusted as well as adjusted estimates depicting the impact of the intervention versus control will be reported along with 95% confidence intervals. The statistical programs R (r-project.org), SAS v9.4 (SAS Institute Inc., Cary, NC), or others will be used for the primary statistical analyses.

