The sample size is based on a mathematical modeling of the intervention on the primary outcome and suggests we should observe an effect size in the intervention arm over the control arm of 43.1%, assuming a rate incidence in our 0-10 yr. old cohort of 1.088 malaria episodes/child/year and 0.619 malaria episodes/child/year in the control and intervention arms, respectively. Using an intra-cluster coefficient of 0.258 and setting the  $\alpha=0.05$ , 6 clusters/arm with a minimum of 48 children/cluster in our child cohort is necessary to detect a significant difference in the rates between the arms with 80% power. In January 2019, the sample size modeling exercise was re-performed because it was learned that villages in the Diebougou health district (the study site) were expected to receive new Interceptor G2 LLINs prior to the 2019 rainy season. These new LLINs are made with two different insecticides (chlorphenapyr and alpha-cypermethrin) to circumvent the prevalent pyrethroid-resistance seen in Burkina Faso the much of SSA. Thus, we assumed a 12%-50% reduction in malaria incidence in both arms due to distribution of these nets. Keeping with an effect size of 43.1% in the intervention arm over the control arm, using an intra-cluster coefficient of 0.2, and increasing the sample size to 100 children/cluster in our child cohort, we need between 4.9 and 5.5 clusters/arm to detect a significant

---

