- **1.3 Sample size and power:** The primary endpoint for the trial is the incidence rate of malaria episodes in children ≤10 years of age as assessed by active case surveillance by study nurses with weekly visits to each child, starting at the first round of MDA and continuing for 4 months in year 1 (1 month after MDA #4), and continuing for another 4 months in year 2 (starting with MDA #5 and ceasing 1 month after MDA #8). The sample size and power for RIMDAMAL II is based on data from our previous trial (RIMDAMAL) and another published trial, IVERMAL. Calculations assume seasonal incidence rates (per year) of approximately 1.088 and 0.619 in the control and intervention arms, respectively, thus corresponding to an incidence rate ratio of 0.619/1.088 = 0.569 (i.e., an incidence rate reduction of 0.431). The initial sample size evaluation shows that RIMDAMAL II has 80% power with 6 villages per arm and 48 children per cluster assuming that the coefficient of variation between clusters is approximately 0.258. During trial initiation, sample size was increased from 12 to 14 villages (7 per arm) with approximately 100 children per village/cluster. The larger sample size provides over 90% power in the detailed simulation studies of the statistical models that were considered for the primary analysis of trial results (Jackson, et al. *Trials* 2021).

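### The January 2019 requirement of 4.9 to 5.5 clusters per arm does not follow from its printed inputs, and its coefficient of 0.2 is unsourced, mislabelled and at odds with the 0.258 kept in the SAP

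*Protocol*

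**What the plan says.** Protocol 10.2 describes two calculations. The first uses a formula for unmatched cluster trials with a rate endpoint, driven by the coefficient of variation of true rates between clusters, "which we estimated in southwestern Burkina Faso to be 0.258", with a citation. The rates are "1.088 malaria episodes/child/year and 0.619 malaria episodes/child/year in the control and intervention arms, respectively". The result is 6 clusters per arm with at least 48 children each, at two-sided 5% significance and 80% power.

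The second, dated January 2019, lowers incidence by 12% to 50% in both arms to allow for new nets. It keeps the 43.1% effect, raises the cluster size to 100 children, and proceeds "using an intra-cluster coefficient of 0.2". Its conclusion is that "we need between 4.9 and 5.5 clusters/arm to detect a significant difference in the rates between the arms with 80% power". Section 10.2 then relies on 7 villages per arm for power above 80%. Section 4 repeats both calculations and gives the 0.258 the same intra-cluster label.

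SAP 1.3 quotes the original rates and a between-cluster coefficient of variation of about 0.258. It does not mention 0.2. For the 14-village design it says: "The larger sample size provides over 90% power in the detailed simulation studies".

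**The concern.** Three things do not fit together. The printed requirement cannot be obtained from the printed inputs. The main variance input falls from a cited 0.258 to an uncited 0.2, with no reason given. And the name used for it belongs to a different quantity: the only intraclass correlation the protocol reports is 0.059.

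This is the protocol's only calculation that supports 7 villages per arm under the new nets. The two departures pull in opposite directions. At 100 child-years per cluster, moving from 0.258 to 0.2 lowers the requirement by about 1.5 clusters per arm, while the unexplained excess raises it by about 1. The printed range therefore looks plausible although it has no derivation a reader can follow, and it disagrees with the SAP on the coefficient.

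**Working it through.** **Inputs.** From Protocol 10.2: z-values 1.96 and 0.84 (the text attaches error-rate wording to them, but they are normal quantiles); rates λ0 = 1.088 and λ1 = 0.619; coefficient k = 0.258, then 0.2; 48, then 100 children per cluster; rate cuts of 12% and 50%; effect 43.1%. Person-time per child is not stated.

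**Formula.** The protocol names the method without printing it. The standard form is

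c = 1 + (1.96 + 0.84)² × X, with X = [(λ0 + λ1)/y + k²(λ0² + λ1²)] / (λ0 − λ1)²

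where y is child-years per cluster and (1.96 + 0.84)² = 7.84.

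**Original design.** With k = 0.258 and y = 48: c = 1 + 7.84 × (0.03556 + 0.10430)/0.21996 = 5.985. With y = 47, c = 6.01. So 48 is the smallest cluster size that fits 6 clusters, exactly as the protocol says. This confirms the formula and shows that one child-year per child was used.

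**January 2019, k = 0.2, y = 100.**

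- 12% cut: λ0 = 1.088 × 0.88 = 0.9574 and λ1 = 0.9574 × 0.569 = 0.5448. c = 1 + 7.84 × (0.01502 + 0.04854)/0.17029 = 3.93.
- 50% cut: λ0 = 0.5440 and λ1 = 0.3095. c = 1 + 7.84 × (0.00854 + 0.01567)/0.05497 = 4.45.

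The protocol prints 4.9 and 5.5.

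**What would give the printed range.**

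| Variant | 12% cut | 50% cut |
|---|---|---|
| As stated | 3.93 | 4.45 |
| Added constant 2 instead of 1 | 4.93 | 5.45 |
| k = 0.241 | 4.94 | 5.46 |
| k = 0.240 | 4.91 | 5.43 |
| 90% power | 4.92 | 5.63 |
| 5 months per child | 4.89 | 6.16 |
| One-sided 5% | 3.30 | 3.72 |

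Only the second and third rows match both ends at one decimal (5.45 is 5.452 before rounding). A coefficient of 0.241 would print as 0.2 at one decimal.

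**At the sourced coefficient, k = 0.258, y = 100.**

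- 12% cut: c = 1 + 7.84 × (0.01502 + 0.08077)/0.17029 = 5.41.
- 50% cut: c = 1 + 7.84 × (0.00854 + 0.02608)/0.05497 = 5.94.

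Both round up to 6 clusters per arm.

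**Dependence on person-time, k = 0.258, 7 clusters per arm.** Inverting the formula gives power = Φ(√(6/X) − 1.96). The person-time values are assumptions.

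| Person-time per child | y | X (12%, 50%) | Power (12%, 50%) |
|---|---|---|---|
| 1 year (the protocol's implied convention) | 100 | 0.563, 0.630 | 90%, 87% |
| 8 months (two 4-month seasons) | 66.7 | 0.607, 0.707 | 88%, 83% |
| 4 months (one season) | 33.3 | 0.739, 0.940 | 81%, 71% |

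For the last row at a 50% cut: √(6/0.940) − 1.96 = 0.57, and Φ(0.57) is about 0.71.

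**The case against.** The best defence is that the printed figure may not be an arithmetic slip. If the coefficient was really about 0.241 and was shortened to 0.2, the unmodified formula gives the printed range. That stands as a possibility, although 0.258 is printed to three decimals in the same section. A reader might infer that the added 1 was counted twice. That fits equally well, and the documents cannot decide between them.

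A reader might also take the intra-cluster label literally. With an intraclass correlation of 0.2 and 100 children, the design effect is 1 + 99 × 0.2 = 20.8, and about 14 to 25 clusters per arm would be needed. The documents do not support that reading. Section 10.2 defines the quantity as SD over mean of cluster rates, Section 4 puts the same label on 0.258, and the true intraclass correlation is reported separately as 0.059. The fault is one of naming.

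Nor can it be said that the SAP's simulated power rests on pre-net incidence. SAP 1.3 ties the original rates to its calculations and does not say which incidence the simulations used.

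Two further points limit the consequences. The SAP keeps 0.258 and cites simulations of the candidate analysis models, so the protocol paragraph is not the only support for 14 villages. And SAP section 3 marks the planned look at net distribution as 2020 only, so a cut in both seasons may be pessimistic.

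**Conclusion.** The point holds as a documentation error. At the printed coefficient of 0.2 the named formula gives 3.9 to 4.5 clusters per arm, not 4.9 to 5.5; the cause cannot be determined. At the sourced 0.258 it gives 5.4 to 5.9, so 6. These results rest on one child-year per child, which the protocol does not state but which its original calculation requires.

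A reader might infer that the trial is underpowered. The documents do not support that: 7 villages per arm exceed the requirement on the protocol's own person-time convention, and at the printed 0.2 the stated requirement is too high rather than too low. The margin does depend on person-time. Power would fall to about 71% only with the 50% cut, a coefficient of 0.258 and just 4 months counted per child. That is an assumption at the low end, because the primary analysis uses both seasons, and SAP 1.3 describes the rates as seasonal, which may mean that one unit per child was intended. The power figures are cluster-level approximations, not results from the planned Poisson mixed model.

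**What to change.** In Protocol Sections 4 and 10.2:

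- Call the quantity the between-cluster coefficient of variation, for both 0.258 and 0.2.
- Use 0.258 and restate the requirement as 5.4 to 5.9, so 6, clusters per arm at 100 child-years per cluster. Alternatively, give the exact value and source of a smaller coefficient with its matching result (3.9 to 4.5 if it is 0.200).
- State the formula's added constant and the person-time assumed per child.

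In SAP 1.3, state which incidence and person-time the simulated power above 90% assumes. I would not insert a recomputed power figure there, because it would depend on person-time that the documents leave open.

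The cost is wording only. The number of villages, the analysis and the conduct of the trial do not change.

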**Figure 3: Modeling of the primary outcome when adding IVM MDA to SMC**

### 10.3. Planned Interim Analyses

#### 10.3.1. Interim Safety Review

AE risk data for each arm following the first MDA round will be accumulated and provided to the DSMB between the 2nd and 3rdMDAs, as well as following the entire first season of MDAs for safety analyses. The DSMB will review the AE compared between intervention and control arms by examining calculated risks ratios and attributable risks with 95% confidence intervals. Serious adverse events (SAE) will be similarly analyzed. The statistical program (e.g. R or SAS or others will be used for the AE statistical analyses. The DSMB will operate under the rules of a DMID-approved charter that will be written at the organizational meeting of the DSMB. The frequency of DSMB meetings, the statistical techniques, rules

and recommendations for stopping guidelines based on AE rates and types, and the types of analyses expected for DSMB reviews/meetings will be defined in the charter.

#### 10.4. **Final Analysis Plan**

The final statistical plan will be written in detail in the finalized standard operating procedure, before the start of the intervention phase, to ensure that the sampling plan (e.g. number of nurse visits, number of mosquitoes and blood samples) collected are appropriate for the intended analyses. In general, standard, two-tailed statistical hypothesis testing  $\alpha=0.05$ , as well as estimating and comparing the effect sizes and confidence intervals, will be used to measure the differences in entomological and parasitological secondary outcomes between arms. The tests used will depend on the type of data collected (e.g., survivorship of blood fed mosquitoes in each arm per collection interval, proportion of mosquitoes parous/arm per collection interval, average counts of trophozoites/slide or counts of the parasite molecular force of infection, sporozoite rates in mosquitoes), and their distributions. These data will also be used to make generalized linear and non-linear mixed effects models in R, SAS or other programs to understand the functional relationships of measured entomological and parasitological variables and the relative contributions of various independent variables on variation in the dependent variable.

## **11. SOURCE DOCUMENTS AND ACCESS TO SOURCE DATA/DOCUMENTS**

All CRFs containing participant demographic and clinical data (active case surveillance data on the children cohort and AE data for all participants) will be entered on password-protected tablets that will be maintained and updated daily by the clinical team working at the field site. This data will be gathered in an electronic data capture system (e.g. REDCap) and be collated and sent encrypted over the internet to be entered into the study database managed by the study data manager(s). Data from participant blood smears will be kept on laboratory notebooks kept by the parasitological team at the IRSS in Burkina Faso, and entered in the same CRFs and study data base by the study data managers. Only the study team will have access to the source data. Long-term maintenance of the participant codes will be held only by the study PIs on password-protected computers and files.

We will permit authorized representatives of the sponsor(s), DMID, and regulatory agencies to examine (and when required by applicable law, to copy) clinical records for the purposes of quality assurance reviews, audits, and evaluation of the study safety and progress.

## **12. QUALITY CONTROL AND QUALITY ASSURANCE**

A detailed quality management plan will be written before the start of the intervention phase of the trial that is in accordance with DMIP guidelines for assuring the quality of the research being conducted. This plan will have standard operating procedures (SOPs) for quality management which describe how the data will be evaluated for compliance with the protocol and for accuracy in relation to source documents. How the documents will be reviewed (e.g., CRFs, notes, product accountability), who is responsible for the reviews, and the frequency for reviews. Methods of training for staff will also be outlined in SOPs and the staff will need to sign off on each training they receive.

The study monitor (CliMAfrica-CRO or other) will verify that the clinical trial is conducted and data are generated, documented (recorded), and reported in compliance with the protocol, ICH/GCP guidelines, and the applicable regulatory requirements. Clinical monitoring reports will be submitted to the investigators, the sponsor, and the DMID.

## 13. ETHICS/PROTECTION OF HUMAN SUBJECTS

### 13.1. Ethical Standard

The investigator will ensure that this study is conducted in full conformity with the principles set forth in The Belmont Report: Ethical Principles and Guidelines for the Protection of Human Subjects of Research of the US National Commission for the Protection of Human Subjects of Biomedical and Behavioral Research (April 18, 1979) and codified in 45 CFR Part 46 and/or the ICH E6; 62 Federal Regulations 25691 (1997).

The trial will also be conducted in compliance with the principles of the Declaration of Helsinki (1996) (<http://www.wma.net/en/30publications/10policies/b3/>), the principles of ICH-GCP, and in accordance with all applicable regulatory requirements by Agence Nationale de Régulation Pharmaceutique (ANRP) within the Burkina Faso Ministry of Health.

The principal investigators and other key personnel have no competing interests or conflicts of interest for the overall trial.

